In alignment with recent health authority guidance, the sponsor is providing options for study -related participant management in the event of disruption to the conduct of the study. This guidance does not supersede any local or government guidelines or requirements or the clinical judgement of the investigator to protect the health and well-being of participants and site staff. If, at any time, a participant's safety is considered to be at unacceptable risk, study intervention will be discontinued, and study follow-up will be conducted.

Scheduled visits that cannot be conducted in person at the study site will be performed to the extent possible remotely/virtually or delayed until such time that on-site visits can be resumed. At each contact, participants will be interviewed to collect safety data. Key efficacy endpoint assessments should be performed if required and as feasible. Participants will also be questioned regarding general health status to fulfill any physical examination requirement.

Every effort should be made to adhere to protocol-specified assessments for participants on study intervention, including follow up. Modifications to protocol-required assessments may be permitted via COVID-19 Appendix after consultation between the participant and investigator, and with the agreement of the sponsor (see below).

The sponsor will continue to monitor the conduct and progress of the clinical study, and any changes will be communicated to the sites and to the health authorities according to local guidance. If a participant has tested positive for COVID 19, the investigator should contact the sponsor's responsible medical officer to discuss plans for study intervention and follow-up. Modifications made to the study conduct as a result of the COVID-19 pandemic should be summarized in the clinical study report.

ADDITIONAL ELEMENTS, WHERE APPLICABLE:

- Certain protocol-mandated visits to the study site may not be possible during the COVID-19 outbreak. Therefore, temporary measures may be implemented if considered appropriate by the sponsor and investigator to maintain continuity of participant care and study integrity. Certain measures, such as those listed below, may be necessary and should be instituted in accordance with applicable (including local) laws, regulations, guidelines, and procedures:
 - remote (eg, by phone / telemedicine) or in-person, off-site (eg, in-home) interactions between site staff (or designees) and participants for study procedures e.g. those related to safety monitoring / efficacy evaluation / study intervention storage and administration (including training where pertinent)
 - laboratory assessments using a suitably accredited local laboratory; for selected measures (eg, urine pregnancy), home testing may be employed
 - other procedures, eg, imaging, may be conducted at an appropriate facility
- Missed assessments/visits will be captured in the clinical trial management system for protocol deviations. Discontinuations of study interventions and withdrawal from the study should be documented with the prefix “COVID-19-related” in the case report form (CRF).
 - other relevant study data elements impacted by the pandemic should also be documented / labeled as “COVID-19-related” in CRFs and / or other study systems, as directed by detailed sponsor guidance. These may include missed / delayed / modified study visits / assessments / dosing, and instances where temporary measures such as those above are implemented.
- The sponsor will evaluate the totality of impact of COVID-19 on collection of key study data and additional data analyses will be outlined in study SAP(s).
- Exclusion: a potential participant with the following features will be excluded from participating in the study protocol:
 - During the 6 weeks prior to baseline, have had ANY of (a) confirmed SARS-CoV-2 (COVID-19) infection (test positive), OR (b) suspected SARS-CoV-2 infection (clinical features without documented test results), OR (c) close contact with a person with known or suspected SARS-CoV-2 infection
 - Exception: may be included with a documented negative result for a validated SARS-CoV-2 test
 - (i) obtained at least 2 weeks after conditions (a), (b), (c) above (timed from resolution of key clinical features if present, e.g. fever, cough, dyspnea)

AND

(ii) with absence of ALL conditions (a), (b), (c) above during the period between the negative test result and the baseline study visit

- NOTES on COVID-related exclusion:

1. If a participant is excluded due to recent COVID-19-related features, the reason for screen failure should be documented in the case report form under the exclusion criterion of having a condition for which participation would not be in the participant's interest or could confound study assessments.

**VERSION HISTORY**

Table [xx] – SAP Version History Summary

SAP Version	Approval Date	Change	Rationale
1		Not Applicable	Initial release

## 1. INTRODUCTION

This statistical analysis plan (SAP) contains the definitions of analysis sets, key derived variables, and statistical methods to evaluate the safety and efficacy of JNJ-67864238 (also known as PTG-200), an experimental drug, in adult participants with moderately to severely active Crohn's disease for Intervention-Specific Appendix (ISA) Protocol JNJ-67864238PACRD2001 that refers to Master Protocol PLATFORMPACRD2001. Analysis results titles, mock-ups and programming instructions for all statistical outputs (tables, figures and listings) will be provided in a separate document entitled Data Presentation Specifications (DPS).

### 1.1. Objectives and Endpoint

#### Objectives

##### Primary Objective

- The primary objective is to evaluate the efficacy of JNJ-67864238 as measured by the change in the Crohn's Disease Activity Index (CDAI) score from baseline at Week 12.

##### Secondary Objectives

- To investigate the safety and tolerability of JNJ-67864238 in patients with moderately to severely active Crohn's disease
- To evaluate the efficacy of JNJ-67864238 to reduce the Simplified Endoscopic Score for Crohn's disease (SES-CD), induce clinical remission, clinical response, and endoscopic healing of the mucosa
- To evaluate the pharmacokinetics (PK), pharmacodynamics (PD), immunogenicity (if applicable), and biomarker response of JNJ-67864238

##### Other Objectives

- to evaluate the efficacy of JNJ-67864238 on patient-related outcomes as measured by the Patient-Reported Outcomes Measurement Information System (PROMIS)-29 score

#### Endpoints

##### Primary Endpoint

- Change from baseline in the CDAI score at Week 12.

##### Secondary Endpoints

- Change in the SES-CD from baseline
- Clinical response as measured by CDAI ( $\geq 100$ -point reduction from baseline in CDAI or CDAI  $< 150$ )
- Clinical remission rate as measured by CDAI (CDAI  $< 150$ )
- PRO-2 remission defined as abdominal pain (AP) mean daily score (AP component of the CDAI) at or below 1 AND stool frequency (SF) mean daily score at or below 3, i.e., AP  $\leq 1$  and SF  $\leq 3$

- Endoscopic response (defined as at least a 50% improvement from baseline in the SES-CD)
- Endoscopic remission (defined as an SES-CD score  $\leq 2$ )

### Other Endpoints

Other endpoints to be evaluated across all post-baseline visits include but are not limited to:

- Change in AP from baseline based on a 0 to 10 numerical rating scale (NRS)
- Change in number of daily loose or watery stools
- Changes from baseline in the CDAI, PRO-2 (the sum of AP and SF subscores of the CDAI score), PRO-3 (the sum of AP, stool frequency, and general well-being subscores of the CDAI score), C-reactive protein (CRP), and fecal calprotectin
- Clinical remission (CDAI  $< 150$ ), PRO-2 remission (AP  $\leq 1$  and SF  $\leq 3$ ), and clinical response based on CDAI
- Endoscopic improvement based on a reduction from baseline in the SES-CD score ( $\geq 3$  points, 25%, 50%)
- Endoscopic healing (defined as the absence of mucosal ulcerations)
- Patient's Global Assessment of Crohn's Disease Activity
- Change from baseline in multivariate score of biomarkers measured in mucosal biopsy samples, whole blood, serum, and/or stool
- Change in PROs as measured by the PROMIS-29 score

## **1.2. Study Design**

The clinical development program for experimental drug in Crohn's disease will be conducted under a platform protocol, which consists of a Master protocol and multiple ISAs. The Master protocol describes the design elements that are common across the whole platform study without any compound information. The ISA describes the specific JNJ-active compound information to evaluate the safety and efficacy of JNJ-active in Participants with moderately to severely active Crohn's disease who have demonstrated an inadequate response or failure to tolerate previous conventional therapy or biologic therapy. This SAP will be in-line follow platform protocol starting from the first ISA phase 2a Proof-of-concept study first. The first ISA is a Phase 2a, multicenter, randomized, double-blind, placebo-controlled study designed to assess the effects of a predominantly gastrointestinal-restricted anti-IL 23R compound for moderately to severely active Crohn's disease. This 12-week Phase 2a study is focused on proof-of-concept and will assess the safety and efficacy of an orally administered high dose of JNJ-67864238 compared with placebo in participants with Crohn's disease. Since the inhibition of the IL-23 pathway has been validated as a mechanism for treating Crohn's disease, a high dose was chosen to assess the efficacy of a locally acting anti-IL-23 inhibitor.

Participants may be biologic intolerant or refractory (Bio-IR) or biologic nonfailures (Bio-NF) populations as defined below:

[figure not shown]
- Bio-IR Population: Those participants who have received infliximab, adalimumab, certolizumab pegol, vedolizumab, or ustekinumab at a dose approved for the treatment of Crohn's disease, and either did not respond initially, responded initially but then lost response, or were intolerant to the medication.

- **Bio-NF Population:** Those participants who have demonstrated an inadequate response to or have failed to tolerate corticosteroids or the immunomodulators 6-MP, AZA, or MTX. Participants who have demonstrated corticosteroid dependence (ie, an inability to successfully taper corticosteroids without a return of the symptoms of Crohn's disease) are also eligible. Bio-NF participants may also have received biologic therapy but only if it was discontinued for reasons other than lack of efficacy or intolerance (eg, a drug holiday).

A target of 90 Bio-IR and Bio-NF participants will be randomized to receive JNJ 67864238 CCI [REDACTED] or placebo in a 3:2 ratio using permuted block randomization, stratified by baseline Crohn's Disease Activity Index (CDAI) score ( $\leq 300$ ,  $>300$ ) and biological refractory status (Bio-IR, Bio-NF). The treatment arms for this study will be as follows: JNJ-67864238 CCI [REDACTED] (N=54) and Placebo (N=36). Of note, the sample size has been chosen to assess a level of efficacy consistent with that observed with systemically available biological therapies for Crohn's disease.

An overview of this study design is presented in [Figure 1](#) below:

**Figure 1:** Schematic Overview of Study Design

## 2. STATISTICAL HYPOTHESES

The hypothesis is that JNJ-67864238 is superior to placebo as measured by the reduction from baseline in the CDAI at Week 12 in Participants with moderately to severely active Crohn's disease.

### Primary Objective

The primary objective is to evaluate the efficacy of experimental drug JNJ-67864238 as measured by the change in the CDAI score from baseline at Week 12.

## Secondary Objectives

The major secondary objectives are as follows:

- To investigate the safety and tolerability of experimental drug JNJ-67864238 in participants with moderately to severely active Crohn's disease
- To evaluate the efficacy of experimental drug JNJ-67864238 to reduce the SES-CD, induce clinical remission, clinical response, and endoscopic healing of the mucosa
- To evaluate the PK, PD, immunogenicity (if applicable), and biomarker response of JNJ-67864238

### 3. SAMPLE SIZE DETERMINATION

The sample size determination is based on the overall population, including both Bio-IR and Bio-NF participants. To examine the hypothesis that JNJ-active is superior to placebo as measured by CDAI, sample size is planned to achieve desirable operating characteristics of a predefined decision-making framework through simulation. A 90 Bio-IR or Bio-NF participants will provide about 90% power when the true treatment difference is 60 (placebo – JNJ-67864238) with standard deviation of 93 in the change in CDAI at Week 12 for both Bio-IR and Bio-NF populations.

### 4. POPULATIONS (ANALYSIS SETS) FOR ANALYSIS

For purposes of analysis, the following analysis sets are defined:

Analysis Sets	Description
Randomized	The randomized analysis set includes all participants who were randomized in the study.
Full Analysis Set (FAS)	All participants who are randomized to a treatment arm within an intervention cohort and receive at least 1 dose of the study intervention
Per Protocol (PP)	The per protocol analysis set (PP) includes a subset of participants in the full analysis set (FAS) who were in compliance with the protocol. Compliance is defined after reviewing by study physician and statistician
Safety	All randomized participants who take at least 1 dose of the study intervention within an intervention cohort. Participants will be analyzed according to the study intervention they actually received
Pharmacokinetics Analysis Set	The PK analysis set is defined as participants who received at least 1 dose JNJ-67864238 and have at least 1 valid blood sample drawn for PK analysis.
Immunogenicity Analysis Set	The Immunogenicity analysis set is defined as participants who received at least 1 dose JNJ-67864238 and have at least 1 valid blood sample drawn for Immunogenicity analysis.

### 5. STATISTICAL ANALYSES

#### 5.1. General Considerations

Descriptive statistics (eg, mean, median, SD, minimum, and maximum) will be used to summarize continuous variables. Counts and percentages will be used to summarize categorical variables. Graphic data displays may also be used to summarize the data. Analyses suitable for categorical data (eg, chi-square tests, Cochran-Mantel-Haenszel chi-square tests, or logistic regression, as appropriate) will be used to compare the proportions of participants achieving selected endpoints

(eg, clinical remission). In cases of sparse events, Fisher's exact test will be considered for treatment comparisons. Continuous response parameters will be compared using a longitudinal model, an analysis of variance (ANOVA) model, or an analysis of covariance (ANCOVA) model. If non-normality is observed, then van der Waerden normal scores will be used to fit a model. For primary endpoint change from baseline in the CDAI score will be fit through a MMRM with categorical effects of population, treatment, time and treatment-by-time, and baseline CDAI score as a continuous covariate as needed, an appropriate external prior information will be incorporated in the form of a prior probability distribution function to evaluate various study hypotheses in a Bayesian framework. In such a framework, inference will be based on posterior probability distributions.

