### 5.3.3. Analysis Methods

#### 5.3.3.1. Main Estimator (Analysis) for the Primary Estimand

The primary analysis will be based on the full analysis set which will include all participants randomized and who receive at least 1 dose of the study intervention. Participants in the efficacy analyses will be summarized according to their assigned treatment arm regardless of whether or not they receive the assigned study intervention. The primary endpoint will be analyzed based on the primary estimand.

Data used in the primary analysis (i.e. the main estimator for the primary estimand) include all values for change from baseline in CDAI score collected up to and including Week 12 for all participants in the primary efficacy analysis set (ie, those who were randomly assigned to study intervention and received at least one dose of study intervention). Any CDAI score collected after experiencing intercurrent event categories 1-3 will be replaced by the baseline observation for CDAI. For subjects experiencing ICE category 4, CDAI data at all visits after an ICE will be set to missing with assumption of missing at random. For ICE category 5, treatment policy strategy, the observed values after ICEs will be used, if available.

The main estimator for the primary estimand is based on the Mixed Effects Model for Repeated Measures (MMRM), under the Missing at Random (MAR) assumption for the missing responses, the missing data will be accounted for through correlation of repeated measures in the model, to test the difference between the experimental group and the placebo group. The analysis will use change in CDAI scores at post-baseline time points through Week 12 as dependent variables. The explanatory variables of the MMRM model will include the fixed, categorical effects of treatment, time, and treatment-by-time interaction, as well as the continuous, fixed covariates of baseline and baseline-by-time interaction. If the intervention cohort includes both Bio-IR and Bio-NF participants, then the biologic therapy status will be included in the MMRM model as well. An unstructured variance-covariance structure will be used to model the within-participant errors. The treatment comparison at Week 12 in terms of the least square mean difference and confidence intervals for decision making will be estimated based on this model.

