#### **5.4.1.3. Analysis Methods for the Estimands for the Major Secondary Endpoints**

The major secondary endpoints of clinical remission (either based on CDAI, SES-CD, or PRO-2), clinical response, endoscopic response, and clinical-biomarker response at Week 12 will be compared between PTG-200 group and the placebo group.

A logistic regression model will be used in the responder analyses with the treatment arm and population status (Bio-IR or Bio-NF), if applicable, as fixed factors, at 2-sided significance level of 0.1. In this model, baseline measurements may be included as covariates as appropriate. The change from baseline in the SES-CD score at Week 12 will be evaluated using MMRM model in comparing treatment difference by LS Mean (SD), LS mean (90% CI). P-Value was based on comparison with placebo model. And other statistical analysis as appropriate.

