### Decision-Making Specifics at the Completion of the Intervention Cohort

The success of the PTG-200 CCI treatment arm is defined as follows:

- Success in change in CDAI: if LB (20%)  $\geq 40$ , ie, the 80% lower confidence bound of the true mean treatment difference at Week 12 is at least 40; or
- Success in change in SES-CD: if LB (20%)  $\geq 0.4$ , ie, the 80% lower confidence bound of the true mean treatment difference at Week 12 is at least 0.4.

The threshold of 40 is selected to provide confidence that a therapy is at least as effective as currently approved therapies (STELARA® [ustekinumab] or adalimumab), where a CDAI change of 40 represents the lower confidence bound for success of the treatment difference between JNJ-67864238 and placebo.

If neither change in CDAI nor change in SES-CD of the PTG-200 CCI treatment arm meets the success criteria, the futility of the PTG-200 CCI treatment arm will be considered. The futility of is defined as follows:

- Futility in change in CDAI: if UB (80%)  $< 60$  and LB (20%)  $< 40$ , ie, the 80% upper confidence bound of the true mean treatment difference at Week 12 is less than 60 and its 80% lower confidence bound less than 40; and
- Futility in change in SES-CD: if UB (90%)  $< 1.6$  and LB (20%)  $< 0.4$ , ie, the 90% upper confidence bound of the true meantreatment difference at Week 12 is less than 1.6 and its 80% lower confidence bound less than 0.4.

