**Attachment 2: Data Simulation**

To evaluate the operating characteristics of the study design, the following assumptions are made based on 3 completed clinical studies (C0743T26/CNTO1275 Ph2b, CNTO1275CRD3001, and CNTO1275CRD3002) conducted by the sponsor:

- The compositions of Bio-IR and Bio-NF populations are 50% each
- For Bio-IR population, the CDAI scores of the JNJ-67864238 [CCI] treatment arm and placebo treatment arm at Weeks 0, 2, 4, 8, and 12 are assumed to be (323,285,259,247,238) and (323,305,300,299,298), respectively. Similarly, for Bio-NF population, the CDAI scores of the JNJ-67864238 [CCI] treatment arm and placebo treatment arm at Weeks 0, 2, 4, 8 and 12 are assumed to be (302,245,208,180,176) and (302,271,254,241,236), respectively.
- The covariance matrix is assumed to be

$$\begin{pmatrix} 3844 & 3069 & 3100 & 3193 & 3255 \\ 3069 & 8100 & 7200 & 6489 & 5670 \\ 3100 & 7200 & 10000 & 7210 & 5250 \\ 3193 & 6489 & 7210 & 10609 & 7030 \\ 3255 & 5670 & 5250 & 7030 & 11025 \end{pmatrix} \quad \text{and} \quad \begin{pmatrix} 3600 & 2970 & 2565 & 3646 & 2520 \\ 2970 & 8100 & 5558 & 5670 & 4725 \\ 2565 & 5558 & 9025 & 6484 & 4988 \\ 3646 & 5670 & 6484 & 11025 & 7166 \\ 2520 & 4725 & 4988 & 7166 & 11025 \end{pmatrix}$$

for the Bio-IR and Bio-NF populations, respectively.

- In CNTO1275CRD3001 and CNTO1275CRD3002, an optional endoscopy substudy was conducted in a subset of study participants. Based on the collected data, change in SES-CD is assumed to have a mixture distribution - excessive zeros (no change) and a normal distribution. Therefore, 2 steps were utilized to simulate the change in SES-CD data.
  - Step 1: no change in SES-CD is simulated for 19% of JNJ-67864238 [CCI] treated participants and 32% placebo treated participants.

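### The normal-scores fallback in SAP 5.1 has no trigger and no exemption for SES-CD change, whose success and futility bounds are set in raw points

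*SAP*

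**What the plan says.** SAP 5.1 sets the general rule: "Continuous response parameters will be compared using a longitudinal model, an analysis of variance (ANOVA) model, or an analysis of covariance (ANCOVA) model". The next sentence is the fallback: "If non-normality is observed, then van der Waerden normal scores will be used to fit a model". It gives no normality test, cut-off, list of endpoints or way back to the original scale.

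The decision bounds are in points. For SES-CD, SAP Attachment 1 calls the final analysis a success if "the 80% lower confidence bound of the true mean treatment difference at Week 12 is at least 0.4". Futility uses upper limits below 1.6 together with lower limits below 0.4, at the final analysis and, with different confidence levels, at the interim. For CDAI, success requires that "the 80% lower confidence bound of the true mean treatment difference at Week 12 is at least 40", and the futility limit is 60. Protocol 9.2.2 has the same numbers but defines the SES-CD bounds on a median difference, where the SAP uses a mean.

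The two endpoints are tied to models differently:

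- **CDAI** (SAP 5.3.3.1): "The analysis will use change in CDAI scores at post-baseline time points through Week 12 as dependent variables", and the "least square mean difference and confidence intervals for decision making will be estimated based on this model".
- **SES-CD** (SAP 5.4.1.3): "The change from baseline in the SES-CD score at Week 12 will be evaluated using MMRM model in comparing treatment difference by LS Mean". The paragraph then allows other analyses as appropriate and does not mention the decision bounds.

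On the expected data, SAP Attachment 2 states that "change in SES-CD is assumed to have a mixture distribution - excessive zeros (no change) and a normal distribution". SAP 5.8 applies the models of its Section 5 at the interim, so the fallback is within reach there too.

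**The concern.** Van der Waerden scores replace each value by a normal quantile of its rank. The treatment effect is then a difference in mean scores and carries no SES-CD points, so a bound of 0.4 or 1.6 points has no meaning for it.

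The rule is written as an instruction, not an option, and the sponsor's own assumptions make non-normal SES-CD data foreseeable. The treatment-failure rule in SAP 5.3.1, which assigns baseline values, adds further zero changes.

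SES-CD matters to the decision. Success on SES-CD alone is enough for overall success, and overall futility requires SES-CD futility. A score difference can also fall close to 0.4, so a comparison on the wrong scale might go unnoticed.

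**Working it through.** **1. The plan's own power figure.** Inputs from SAP 3 and 1.2: difference 60, SD 93, arms of 54 and 36, two-sided alpha 0.1 (SAP 5.3). SE = 93 × √(1/54 + 1/36) = 20.0. Power = Φ(60/20.0 − 1.645) = Φ(1.35) = 91.2% (90.8% with the t distribution). The stated figure of about 90% reproduces.

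**2. Range of the score scale.** Score = Φ⁻¹(rank/(N+1)). At N = 90 the largest is Φ⁻¹(90/91) = 2.29, so no difference can exceed 2 × 2.29 = 4.58. At the interim (N = 45) the limit is 4.04. CDAI bounds of 40 and 60 are out of reach on this scale; SES-CD bounds of 0.4 and 1.6 are numerically reachable but mean something else.

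**3. SES-CD on the raw scale, in closed form.** Inputs from SAP Attachment 2, half Bio-IR and half Bio-NF; z is the share of excess zeros.
- Mean improvement, (1 − z) × |μ|. Bio-IR: 0.81 × 3.26 − 0.68 × 0.22 = 2.49. Bio-NF: 0.88 × 4.68 − 0.88 × 2.71 = 1.73. Average difference: 2.11 points.
- Variance, (1 − z)(σ² + μ²) − [(1 − z)μ]², ignoring rounding. Active: 13.3 (Bio-IR) and 33.0 (Bio-NF), average 23.1. Placebo: 9.8 and 31.4, average 20.6.
- SE = √(23.1/54 + 20.6/36) = 1.00.
- Success: Φ((2.11 − 0.4)/1.00 − 0.85) = Φ(0.86) ≈ 81%.
- Futility: Φ((1.6 − 2.11)/1.00 − 1.29) = Φ(−1.80) ≈ 4%.

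**4. Simulation of the switch.** 5000 trials from Attachment 2, 54:36, with a Week 12 linear model fitted to raw change and to scores, and the Attachment 1 final bounds applied unchanged. The SES-CD model has treatment and population; the CDAI model adds baseline CDAI.

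| Under the alternative | Raw points | Scores |
|---|---|---|
| SES-CD mean estimate | 2.12 | 0.42 |
| SES-CD success | 80.0% | 23.4% |
| SES-CD futility | 3.4% | 76.6% |
| SES-CD power, two-sided 0.1 | 66.4% | 67.9% |
| CDAI success | 55.6% | 0% |
| CDAI futility | 20.0% | 100% |
| CDAI power, two-sided 0.1 | 90.2% | 89.8% |

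The raw SES-CD figures agree with step 3. Power barely moves, so the damage is to the scale and not to the test. On scores, SES-CD success and futility sum to 100%: the 1.6 limit never binds, and the inconclusive zone (100 − 80.0 − 3.4 = 16.6% on raw points) disappears. The CDAI rows show only what a literal switch would do; see the objection.

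**5. How often the switch would occur.** The SAP names no test, so Shapiro-Wilk p < 0.05 on model residuals is my assumption. For SES-CD it fires in 38% of trials under the alternative and 60% under no difference. For CDAI it fires in about 5% under the planned normal model. If 10%, 20% or 30% of participants are set to zero change as treatment failures (an assumed range), the CDAI rate is 11%, 34% or 70%.

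**6. Averaging over trials that do and do not switch.** The shifts in step 4 assume that every trial switches. If triggering were unrelated to the result, SES-CD success under the alternative would average 0.38 × 23.4% + 0.62 × 80.0% ≈ 58%, and SES-CD futility 0.38 × 76.6% + 0.62 × 3.4% ≈ 31%.

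**The case against.** The strongest reply is that specific text overrides a general section. SAP 5.3.3.1 models change in CDAI and takes the decision-making intervals from that model. SAP 5.4.1.3 names an LS-mean MMRM for SES-CD, and its closing words on other analyses add to that model without replacing it. Attachment 1 defines the bounds on a mean difference, which fixes the units. The 5.1 rule concerns how responses are compared and can be read as changing only the test. The framework is also non-binding, and the protocol plans an additional assessment on CDAI alone, so an SES-CD ambiguity need not block a decision.

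For CDAI this reply succeeds. A reader might infer from 5.1 that the 40 and 60 point bounds lose their scale. The documents do not support that, because 5.3.3.1 keeps points for decision making.

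For SES-CD it succeeds only in part. A reader might infer that the SES-CD half of the rule cannot be evaluated at all; that is too strong, since 5.4.1.3 does name a point-scale model. But no sentence says that this model supplies the bounds, none exempts them from the fallback, and the p-value-only reading is not written down.

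Two further inferences should be avoided. The trigger is foreseeable but not certain, and its rate depends on a test the SAP does not name. And no passage says when normality would be assessed, so a pre-test after unblinding is not established. The Master protocol, to which Protocol 9.4 defers, and the separate interim analysis plan were not available; either might restrict the fallback.

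**Conclusion.** The point holds for SES-CD change as a gap worth closing before unblinding. A stated rule, followed literally, yields an estimate on a scale that the 0.4 and 1.6 point bounds cannot use, for an endpoint the SAP itself expects to be zero-inflated. For CDAI it is a conflict of wording between SAP 5.1 and 5.3.3.1.

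The size rests on Attachment 2 being right, on an assumed normality test, and on someone applying the unchanged bounds to score units. The simulation uses mean-based SES-CD bounds, treats SES-CD as independent of CDAI and has no interim look. On raw points it gives overall success of 91% under the alternative and 10% under no difference, against the protocol's 87% and 5%. It therefore does not reproduce the protocol's operating characteristics, and only the contrast between the two scales should be used.

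**What to change.** Add to SAP 5.1, and repeat in 5.4.1.3, that estimates and decision bounds for SES-CD change, and for consistency CDAI change, always come from a raw-point model at both the interim and the final analysis. If residuals are non-normal, use bootstrap or robust standard errors. Normal scores then serve only for a supportive p-value, under a stated normality criterion.

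In the same edit, reconcile the SES-CD measure between Protocol 9.2.2 (median difference) and SAP Attachment 1 (mean difference), and name the matching estimator. An LS-mean model fits a mean bound; a median bound needs a raw-point median estimator.

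The cost is a few sentences in the SAP and slightly more analysis work. No extra data are needed.
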